1.4.2 The Nijmegen Haemostasis Assay (NHA)

Although thrombin generation reflects the patients' coagulation status, it does not entirely represent the in vivo situation of the patient because it does not take fibrinolysis into account. The NHA uses two fluorescent substrates with non-interfering fluorescent excitation and emission spectra to measure both thrombin and plasmin generation in a single well by a fluorimeter. [60] The assay has been shown to be sensitive for severe haemophilia A, reflected by severely diminished thrombin generation and, due to lack of TAFI activation, increased plasmin generation. Moreover, the assay is also sensitive for FV Leiden, the poly A prothrombin mutation and variations in Protein C and S activity. [60, 61]

1.4.3 Misclassification of disease severity by the one-stage clotting assay in haemophilia B patients

FVIII and FIX activity is most often assessed using the one-stage clotting assay. [62] Several studies have observed a discrepancy in factor VIII activity between the one-stage clotting assay and the chromogenic assay in patients with mild and moderate haemophilia A. More specifically, a higher factor VIII activity was found with the one-stage assay, compared to the chromogenic assay. [63-67] Several studies have found that certain FVIII mutations are associated with this discrepancy. [64, 67, 68]

Misclassification of disease severity by the use of the one-stage clotting assay could have important ramifications; patients could be designated as having a milder bleeding risk, potentially leading to undertreatment of patients. All almost studies have focused on haemophilia A, with the exception of one recent conference paper [69] which also found a discrepancy between the one-stage clotting

assay and the chromogenic assay.

Given the scarcity of evidence for this phenomenon in the haemophilia B population, the HIN-6 study will assess the extent of misclassification of disease severity by re-evaluating the baseline FIX activity using the chromogenic FIX assay in all haemophilia B patients.

1.4.4 Validating the iCHEC paediatric bleeding assessment tool

We will also describe bleeding scores in children using the newly developed paediatric bleeding assessment tool (iCHEC), in all children with haemophilia, and in subgroups according to haemophilia severity, age and treatment regimen (prophylaxis/on demand). Bleeding scores are expected to be higher among children with severe haemophilia as compared to children with moderate or mild haemophilia, higher in on-demand treated patients compared to patients on prophylaxis and higher with increasing age.

1.5 The immune response to FVIII

1.5.1 The humoral immune response to FVIII

The development of neutralizing antibodies against FVIII (inhibitor formation) is the most severe complication of treatment for haemophilia A patients. Antibodies against functional sites on the FVIII molecule (neutralizing antibodies) can be detected with the Bethesda assay. However, the Bethesda assay cannot detect antibodies against non-functional sites on the FVIII molecule (non-neutralizing antibodies). Alternative techniques such as ELISA [70] can detect a broader range of FVIII-specific antibodies. However, until recently these assays were not able to discriminate between neutralizing and non-neutralizing antibodies, this limited their usefulness in research and clinical practice.

Recently, several studies have shown that antibodies of the IgG4 subclass are more prevalent among patients with neutralizing antibodies, compared to patients with non-neutralizing antibodies. [70] In addition, by using a novel ELISA platform, Hofbauer et al found that they were able to discriminate between neutralizing and non-neutralizing antibodies based on the presence of high-affinity FVIII-specific antibodies. [71]

It is as of yet unclear how FVIII-specific non-neutralizing antibodies could influence the clinical course of disease. One longitudinal study in previously untreated patients (PUPs) by Cannavò et al

found that the presence of non-neutralizing antibodies before the first administration of FVIII was a risk factor for inhibitor formation. [72] There might also be a relationship between the presence of non-neutralizing antibodies and FVIII clearance. Recently, Hofbauer et al [73] conducted a study in which a significant association was found between the presence of FVIII-specific IgG non-neutralizing antibodies and a shorter FVIII half-life.

As of yet, most studies on this subject are small and/or cross-sectional in nature, therefore, the HiN-6 study will assess the prevalence and characteristics of FVIII-specific non-neutralizing antibodies. In addition, The HiN-6 study will also assess the impact of non-neutralizing antibodies on inhibitor development, FVIII activity/antigen levels, joint bleeds and increased FVIII clearance. The HiN-6 will also assess possible misclassification of low-titre inhibitors as non-neutralizing antibodies using a low-titre inhibitor assay (([name], personal communication).

1.5.2 The cellular immune response to FVIII

The primary immune response to FVIII is initiated by antigen presenting cells (APCs). The first step, namely antigen presentation by APCs to CD4+ T-cells, is dependent on the presence of a proinflammatory micro-environment. The FVIII molecule is proteolytically processed into small peptides, loaded onto the MHCII molecule and presented on the APC cell surface. Subsequent activation of CD4+ T-cells requires upregulation of co-stimulatory molecules CD40 and CD80/86 and pro-inflammatory cytokine production by the APC. [74]

T-effector cells (Teffs) stimulated in this manner can induce an immune response by using cytokines and surface molecules. In contrast to Teffs, CD4+ CD25+ FoxP3+ T-regulatory cells (Tregs) can also suppress an immune response through cytokine production (IL-10 or TGF-beta) and cell-to-cell contact. The specific type of T-cell response is most likely determined by the environmental context of antigen presentation the APC.

Several experimental animal studies have found an association between high Treg to Teff ratios and a decreased risk of FVIII-specific antibody formation. Miao et al found that FVIII-deficient mice that overexpress CD4+ FOXP3-positive regulatory T-cells did not develop FVIII antibodies after plasmidmediated F8 gene transfer. [75] In addition, Waters et al found that administering antiCD3 antibodies in haemophilic inhibitor mice resulted in a higher of ratio of splenic Tregs to Teffs. This effect was associated with a decrease in both inhibitor incidence and anti-FVIII antibody titres when

compared to controls. [76]

We hypothesize that natural differences in the APC response to FVIII can result in a higher Treg to Teff ratio, this in turn will lead to less FVIII-specific antibody formation. The HiN-6 study aims to identify novel immunological risk factors for the development of FVIII-specific antibodies by assessing both the APC response to FVIII and the subsequent T-cell response.

Chapter 2 – General and specific objectives of the HiN-6 study

This chapter describes the five general objectives and their accompanying specific objectives.

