- To characterize all FVIII-specific antibodies with respect to Ig class, IgG subclass and affinity, and to evaluate whether some of these characteristics are more associated with having neutralizing antibodies (inhibitors) rather than non-neutralizing antibodies (NNAs).

Secondary objectives:

- 1. To assess whether F8 genotype and polymorphisms in immune response genes influence the development of non-neutralizing antibodies (NNAs).
- To assess whether F8 genotype and polymorphisms in immune response genes influence the development of either neutralizing antibodies (inhibitors) or non-neutralizing antibodies (NNAs).
- 3. To evaluate the association between non-neutralizing antibodies (NNAs) and bleeding frequency in patients with severe haemophilia A.
- 4. To evaluate potential misclassification of low-titre inhibitors as non-neutralizing antibodies

in patients with haemophilia A.

5. To evaluate the diagnostic performance of a modified FVIII ELISA for detection of FVIIIspecific antibodies (inhibitors), using the Bethesda assay as the reference test.

2.5.2 Specific objectives assessing dendritic cell response and T-cell activation in the FVIII immune response:

Primary objectives:

[figure not shown]
- To compare the expression of interleukin-2 and TGF-beta in monocyte-derived dendritic cells after stimulation with FVIII with and without danger signals (e.g. LPS) in patients with nonneutralizing FVIII-specific antibodies (NNAs) and patients without any current FVIII-specific non-neutralizing antibodies.
- To compare the regulatory T- cell count, as a proportion of all CD4+ T-cells in patients with non-neutralizing FVIII-specific antibodies (NNAs) or patients without any current FVIIIspecific antibodies.

Chapter 3 - Study design

HiN-6 study design

The HiN-6 study will consist of both cross-sectional and longitudinal observational studies, according to the specific research objective. A mixed-methods approach will be used for data collection and analysis. All participants will be asked to fill out a questionnaire and to provide a blood and urine sample. In addition, information will be obtained from medical records. For some of the planned substudies, a smaller number of patients will be asked to provide an additional blood sample at a second visit. Detailed study procedures can be found in chapter 5.

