- Bethesda assay: We will measure the presence of inhibitors using the Bethesda assay with Nijmegen modification. A titre of at least 0.6 Bethesda Units is required to be positive for this assay. The cut-off point for low-titre vs high-titre inhibitors is 5.0 Bethesda Units. [92]
- Low-titre inhibitor assay: To assess the presence of low-titre inhibitors, we will use a lowtitre inhibitor assay. ([name], personal communication)
- ELISA: We will assess the presence and characteristics of FVIII-specific antibodies in our full cohort using a highly sensitive and fully validated ELISA platform developed by Whelan et al.
 [70] In patients who are positive for antibodies using this assay we will characterize the isotype (IgA, IgM and IgG) and for the IgG isotype also the subclass (IgG1 to 4). Samples with confirmed specificity for FVIII will also be assessed for apparent affinity.

The apparent affinities of FVIII-specific antibodies for all immunoglobulin isotypes and IgG subclasses will be assessed using a competition-based ELISA approach by Hofbauer et al. The affinity assessment is based on the availability of antibody for binding to FVIII-coated ELISA plates after competition with FVIII in solution. [71]

• Other laboratory tests such as:

- FVIII and FIX activity using one-stage assay
- FVIII and FIX activity using chromogenic assay
- FVIII and FIX antigen level
- FVIII genotype (if unknown)
- FVIII haplotype
- HLA/IL-10/TNFα/CTLA4/HO-1/FcgR gene variants

Second visit (50 adult participants):

Based on the results of the first analyses, we will draw an additional 50 mL of blood in 50 selected participants during a second visit to the haemophilia treatment centre. This second sample will be only be used for this substudy and will not be stored in the biobank. Blood samples will be used for the following experiments: • **Regulatory T cell count:** Regulatory T cell count will be assessed using both flow cytometry and a quantitative real-time PCR assay developed by Epiontis (Epiontis Treg assay).

Flow cytometry

After stimulation of PBMCs with FVIII, we will quantify all T-cell subsets using flow cytometry. PBMCs will be stained with monoclonal antibodies against cell receptors specific for a certain T-cell subset (e.g. CD4+, CD25high, CD127low, FOXP3+ for T-regulatory cells) [93] and markers of T-cell activation (e.g. CD154) [94].

Epiontis Treg assay

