Endpoint: The presence or absence of NNAs will be used as the endpoint (coded as a dichotomous variable). Firstly, The Bethesda assay will be used to assess inhibitor presence. If negative, an ELISA will be used to detect the presence of NNAs.

Statistical analysis: We will use logistic regression to evaluate the association between interleukin-2 and the presence of NNAs and the relationship between TGF-beta and the presence of NNAs. In addition, we will examine the combined effect of increased expression of interleukin-2 and TGF-beta on the presence of NNAs using logistic regression.

Primary objective 2: To compare the regulatory T- cell count, as a proportion of all CD4+ T-cells in patients with non-neutralizing FVIII-specific antibodies (NNAs) or patients without any current FVIII-specific antibodies.

Study design and population: A case-control study design will be used. The cases will consist of 25 severe patients with NNAs that never underwent ITI. The controls will consist of 25 severe patients without any current NNAs that never underwent ITI. All haemophilia patients must have a F8 intron-22 inversion mutation. Haemophilia patients with current or previous inhibitors are excluded. **Determinant:** T-regulatory cell count, as a proportion of all CD4+ T-cells will be used as the determinant. T-regulatory cell count will be assessed using both flow cytometry and a quantitative real-time PCR assay developed by Epiontis (Epiontis Treg assay).

Potential confounders: We will potentially adjust for the previous number of EDs to FVIII, FVIII genotype and family history of inhibitor formation as well as other potential genetic determinants such as HLA, IL-10, TNF α , CTLA4, HO-1 and FcgR gene polymorphisms.

Endpoint: The presence or absence of NNAs will be used as the endpoint. Firstly, The Bethesda assay will be used to assess inhibitor presence. If negative, an ELISA will be used to detect the presence of NNAs.

Statistical analysis: We will use logistic regression to evaluate the association between the dendritic cell cytokine response and the presence/absence of NNAs

Chapter 7 - Ethical considerations

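### The cellular substudy hypothesizes a chain from APC response through the Treg:Teff ratio to antibodies, but no planned analysis links APC response to T-cells, Teff is never a variable, and the Treg objective has no model of its own

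*Protocol*

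**What the plan says.** **Hypothesis (Protocol 1.5.2).** "We hypothesize that natural differences in the APC response to FVIII can result in a higher Treg to Teff ratio", and the protocol expects this to reduce FVIII-specific antibody formation. The sentence that follows gives the aim as finding immunological risk factors by "assessing both the APC response to FVIII and the subsequent T-cell response".

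**Objectives (Protocol 2.5.2).** Objective 1 compares dendritic cell expression of interleukin-2 and TGF-beta between patients with and without NNAs. Objective 2 reads: "To compare the regulatory T- cell count, as a proportion of all CD4+ T-cells in patients with" NNAs or without antibodies.

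**Data (Protocol 5.1.2, second visit).** One extra sample from 50 adults feeds both assays. After FVIII stimulation "we will quantify all T-cell subsets using flow cytometry", with staining for "markers of T-cell activation (e.g. CD154") as well as Treg markers. Monocyte-derived dendritic cells (moDCs) are cultured, stimulated with FVIII and assessed for cytokine response.

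**Analysis (Protocol 6.5.2).** Both objectives use 25 cases with NNAs and 25 controls without. Under objective 2, "T-regulatory cell count, as a proportion of all CD4+ T-cells will be used as the determinant", and "The presence or absence of NNAs will be used as the endpoint". The analysis sentence under objective 2 then specifies a logistic regression of NNA status on the dendritic cell cytokine response.

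**The concern.** The hypothesis has two links: APC response to T-cell balance, and T-cell balance to antibodies. The first is never analysed. For the second, the stated determinant is a different quantity from the one hypothesized, and the model sentence names another variable altogether.

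Two misreadings could follow. A null result for the Treg share could be taken as evidence against a hypothesis about the ratio. Two separate associations with NNA status could be taken as support for a chain whose middle was never examined. If the ratio or the APC-to-T-cell link is analysed later, it will be post hoc, although the measurements were planned from the start.

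**Working it through.** **1. Sample size.** 25 cases + 25 controls = 50, which agrees with the 50 second-visit participants in 5.1.2. The protocol gives no power calculation for this substudy, so there is none to reproduce.

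**2. Links against analyses.**

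| Step in 1.5.2 | Measured (5.1.2)? | Analysed (6.5.2)? |
|---|---|---|
| APC response → T-cell balance | Both, same 50 patients | No; NNA status is the only endpoint |
| Treg:Teff ratio → antibodies | T-cell subsets and activation markers | Ratio never named; Treg share is the determinant |
| Treg share → NNA | Flow cytometry and PCR | Determinant named; the model sentence names the dendritic cell response |
| APC response → NNA | Yes | Yes (objective 1, repeated under objective 2) |

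**3. Can the Treg share stand in for the ratio?** Let p be the Treg share of CD4+ cells and f the share of non-Treg CD4+ cells that count as effectors. Then ratio = p / ((1 − p) f). With p = 0.05 (assumed):
- f = 1: 0.05/0.95 = 0.053
- f = 0.5: 0.105
- f = 0.2: 0.263
- f = 0.1: 0.526

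At f = 1 the ratio is p/(1 − p), which carries the same information as the share. Otherwise they differ. With an assumed SD of log share of 0.3 and SD of log f of 0.2, 0.4 or 0.8, log share and log ratio correlate 0.85, 0.62 or 0.37.

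**4. Illustrative power, 25 against 25, two-sided 5% t-test.** All inputs are assumptions: Tregs 5% of CD4+; reactive effectors e = 0.1-1% of CD4+; SD 0.3 for log share and 0.8-1.2 for log ratio.

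*Only effectors differ, k-fold higher in cases.* New share = 0.05/(1 + (k − 1)e).
- e = 0.001, k = 2: 4.995%. e = 0.01, k = 3: 4.902%.
- Largest standardised difference: ln(0.05/0.04902)/0.3 = 0.066. Power is 5.0-5.6%.
- Ratio, twofold: ln 2 = 0.69, divided by 0.8, 1.0, 1.2 = 0.87, 0.69, 0.58. Power 85%, 67%, 52%.
- Ratio, threefold: ln 3 = 1.10, giving 1.37, 1.10, 0.92. Power over 99%, 97%, 89%.

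*Only Tregs differ, 25% lower in cases.* −ln 0.75 = 0.288.
- Share: 0.288/0.3 = 0.96. Power 91%.
- Ratio: 0.288/0.8 to 0.288/1.2 = 0.36 to 0.24. Power 24% to 13%.

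Neither measure dominates.

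**5. How to fit the missing APC-to-T-cell model.** Patients are sampled on NNA status, which under the hypothesis is a consequence of the ratio. Adjusting for it conditions on a downstream variable. In a simulation with a true slope of 0.5 (assumed NNA prevalence 6-50%, log-odds 0.7-1.6 per SD of ratio), the adjusted slope fell to 0.38-0.49. Weighting by the inverse sampling fractions recovered 0.50.

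**The case against.** **The chain is background; the objectives follow the aim.** The aim in 1.5.2 is to find risk factors, and relating one APC measure and one T-cell measure to NNA status does serve it. This stands in part and keeps the severity moderate. But the aim directly follows the hypothesis and speaks of the T-cell response as subsequent to the APC response, and nothing examines that sequence.

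**Extra exploratory models can be left to a SAP.** True of detail. Here, however, the protocol itself fixes determinant, endpoint and model for each objective; these do not match its hypothesis, and one model sentence does not match its own determinant.

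**Teff is not defined.** This stands. A reader might infer that Teff means FVIII-reactive CD154+ cells. Section 1.5.2 says only that these are T-cells stimulated through antigen presentation, and CD154 is given as an example marker. If Teff were all non-Treg CD4+ cells, share and ratio would be equivalent (step 3). The missing APC-to-T-cell analysis remains either way.

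**The animal evidence is not only about the ratio.** Also correct. Of the two mouse studies described, one concerns Treg overexpression and one the ratio. The Treg share is therefore a reasonable determinant to keep.

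**Conclusion.** The point holds as a mismatch between the hypothesis and the written plan, and it can be repaired cheaply. Three facts rest on the text alone: no analysis relates APC response to a T-cell measure, Teff and the ratio are never variables, and no model for the Treg determinant is written.

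Stronger readings are not supported. A reader might infer that the study cannot test its hypothesis; that is true of the plan as written, not of the data it will collect. A reader might also infer that the study would find nothing even if the hypothesis were true. That holds only if the difference lies in a small effector population; if Tregs change, the share is the more sensitive measure. The power figures are illustrations on assumed inputs. Nor would the added analyses prove the mechanism: sampling is cross-sectional, in patients who already have or lack NNAs.

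**What to change.** 1. **Protocol 6.5.2, objective 2:** correct the analysis sentence to a logistic regression of NNA status on the Treg share of CD4+ cells.
2. **Protocol 2.5.2 and 6.5.2, objective 2:** define Teff from the planned flow panel before data are seen. Add the log Treg:Teff ratio as a prespecified determinant beside, not instead of, the Treg share.
3. **Protocol 6.5.2:** add linear regressions of the log ratio and of the Treg share on the moDC cytokine response. Weight cases and controls by the inverse of their sampling fractions, taken from the counts of eligible patients with and without NNAs in the first-visit cohort. Keep the model adjusted for case status as a sensitivity analysis only.

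**Cost:** protocol wording and a few extra models, with no new blood or assays. There are more exploratory tests, and the ratio is noisier than the share. Weighting loses precision when NNAs are rare: the effective sample size is 25/(q² + (1 − q)²) for prevalence q among eligible patients, which is 50 at q = 0.5 but 25/(0.0036 + 0.8836) = 28 at q = 0.06. The eligible counts must be recorded when the 50 are selected.

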2.1 General objective: Describing the health status of the Dutch haemophilia population

2.1.1 45 years of haemophilia treatment in the Netherlands, 1972-2017

Main objectives:

- To describe changes in bleeding, factor consumption, bleeding-induced joint damage, inhibitor formation, HIV/HCV infection as well as cause-specific and all-cause mortality among Dutch PWH for the period 1972-2017.
- 2. To describe the prevalence of several haemophilia-related and non-haemophilia related comorbidities in the Dutch haemophilia population and to compare these results with the general Dutch male population.
- 3. To describe the uptake, efficacy and safety of hepatitis C treatment in PWH currently or previously infected with hepatitis C.

2.1.2 Physical activity, sports and health outcomes

Main objectives:

- 1. To assess sports participation according to age and haemophilia severity and compare this to the general population.
- 2. To assess the association of the amount and type of sports practice with bleeding

frequency, self-reported activities , self-reported physical performance and joint function.

2.2 General objective: To assess health-related quality of life of PWH in the Netherlands

2.2.1 General quality of life

Main objectives:

- 1. To describe health-related quality of life in all PWH in the Netherlands over time since 1992.
- To quantify the association between health-related quality of life and disease severity, degree of arthropathy, bleeding phenotype, pain and pain coping, self-reported joint function and ability to self-manage in patients with mild, moderate or severe haemophilia.
- To quantify the relationships between health-related quality of life and the prevalence of social determinants of health, including participation and social functioning, ability to work, education and relationships patients with haemophilia. These study questions will also be separately assessed in the older population (>50yr)
- 4. To assess the incidence of falls and the prevalence of fear of falling in older adults (>65 years of age) with haemophilia.
- 5. To assess the incidence of a false-positive result of the self-administered faeces test in the colon cancer screening test in adults with haemophilia between 55 and 75 years of age.
- 6. To assess the incidence of abnormal results of the additional colonoscopy in people with haemophilia compared to the general population.

